## Overview of Amendments integrated in the protocol text of Version 4.1 of 04-MAR-2020

Amendment No / CSP Version	Date	Sections concerned	Rationale
1 / CSP V2.0	26-Apr-2018	Signature Page, Synopsis, 2, 3, 4, 6, 7, 8, 9, 10	Introduction of a new Biostatistician. Update with clarification of wording, corrections and formatting. Revision of the protocol to eliminate inconsistencies between different protocol sections.
1 / CSP V2.0	26-Apr-2018	Flowchart, 3, 7, 9	Clarification regarding the time-period between screening and baseline and the need of repeated assessments and diagnostic tests at these visits.
1 / CSP V2.0	26-Apr-2018	Synopsis, 4	Incomplete exclusion criterion 4 was complemented.
1 / CSP V2.0	26-Apr-2018	3	Clarification of treatment algorithm.
1 / CSP V2.0	26-Apr-2018	6	Clarification of treatment algorithm resulted in a revised definition for prohibited medication (section 6.10). Restructuring of section 6.11 'Warnings and Precautions'.
1 / CSP V2.0	26-Apr-2018	9, 11	Update and clarification regarding the handling of laboratory samples and the assessment of results.
2 / CSP V3.0	07-Jun-2019	Signature page, Introduction, 4	Introduction of a new Biostatistician PPD . Update with clarification of wording, corrections and formatting.
2 / CSP V3.0	07-Jun-2019	Synopsis, Flowchart, 3, 4, 7, 9, 10	Intra-operative inclusion criterion was adapted. Based on patients' bodyweight and clinical condition, the clinical need of FFP transfusion during surgery can already occur after a clinically relevant bleeding of approximately 1 liter. Instead of measurement and calculation of blood loss prior to the 'decision to treat', in case of a clinically relevant bleeding an
			estimation of blood loss will take place.
2 / CSP V3.0	07-Jun-2019	4.2	Inclusion criterion 4 aims to ensure that only patients without hereditary bleeding disorders are to be included in this study. Therefore, a footnote for clarification of wording was included.
2 / CSP V3.0	07-Jun-2019	Synopsis, Flowchart, 3, 6, 7, 9	The dosage was adapted in order to avoid under-dosing of subjects. The first BT524 treatment was changed to a minimum dose of 2 g. The option for repeated dosing with IMP was included. The wording of the

Amendment No / CSP Version	Date	Sections concerned	Rationale
			secondary endpoints was adapted accordingly.
			The dose justification was updated.
2 / CSP V3.0	07-Jun-2019	Flowchart, 7	The time points '90 minutes after treatment start' and 'end of the surgery' can be close together. In this case, blood samples do not have to be taken at both times. Update with clarification of wording. The option for repeated dosing with IMP was included.
2 / CSP V3.0	07-Jun-2019	7	Clarification of wording regarding the re- screening of subjects.
2 / CSP V3.0	07-Jun-2019	9.3, Appendix 2	Update and clarification regarding the definition of Adverse Events of Special Interest (AESI) and the respective reporting procedures.
3 / CSP V4.0	04-Dec-2019	Cover Page, Signature page, 1, 9	Introduction of a new Biostatistician PPD . General update with clarification of wording, corrections and formatting.
3 / CSP V4.0	04-Dec-2019	Synopsis, Flowchart 2, 3, 5, 7.2, 8.1	Study synopsis, study objectives and study design have been modified to extend the target population of the study to allow inclusion of subjects undergoing pseudomyxoma peritonei surgery (only applicable in the United Kingdom) and to introduce the active comparator cryoprecipitate in this treatment group.
3 / CSP V4.0	04-Dec-2019	4.1 and 4.2, 6.6	Update in order to take particular account of subjects with pseudomyxoma peritonei.
3 / CSP V4.0	04-Dec-2019	Synopsis, 3, 4.2, 6.1, 6.6, 7	Clarification of wording of the intra-operative inclusion criterion.
3 / CSP V4.0	04-Dec-2019	Synopsis, 10	Update with clarification of wording and revision to include interim analyses.
			Following the Data Monitoring, the assumed standard deviation has been adjusted and the power has been reduced.
3 / CSP V4.0	04-Dec-2019	19	Update of scientific literature mainly regarding the inclusion of subjects with pseudomyxoma peritonei.
4 / CSP V4.1	04-Mar-2020	Cover Page, Signature page	Introduction of a new Biostatistician PPD .
4 / CSP V4.1	04-Mar-2020	Synopsis, Flowchart, 3, 4, 5, 6, 7.1, 9, 10.9	Study synopsis, study design and study treatment have been modified to describe in detail the treatment of subjects undergoing pseudomyxoma peritonei surgery in the United Kingdom.

Amendment No / CSP Version	Date	Sections concerned	Rationale
			General update with clarification of wording, corrections and formatting.
4 / CSP V4.1	04-Mar-2020	Study Population 4.1	Update in order to take particular account of subjects with pseudomyxoma peritonei.
4 / CSP V4.1	04-Mar-2020	IMP 5.3	Detailed description of the active comparator cryoprecipitate.
4 / CSP V4.1	04-Mar-2020	Methods for Assessing Primary Efficacy Parameter, 9.1.2	Adaption of process for quantification of blood loss due to cytoreductive PMP surgery.
4 / CSP V4.1	04-Mar-2020	Laboratory Parameters, 9.2.1, Table 1	Introduction of two additional laboratory parameters to be analysed in PMP subjects, update of Table 1.
4 / CSP V4.1	04-Mar-2020	Assessment of Adverse Events, 9.3.4	Update of section "Responsibilities of Sponsor" to clearly specify where to find the Reference Safety Information of both, BT524 and cryoprecipitate.
5 / CSP V4.2	04-Aug-2020	Synopsis, 2, 3, 4.1, 4.2, 5.2, 6.6, 7.2, 9.2.1.4, 10.3	General update to clarify that in the United Kingdom (UK) only one site will be involved and only subjects undergoing cytoreductive surgery for PMP can be included.
			Removal of information regarding the treatment of subjects undergoing spinal surgery.
5 / CSP V4.2	04-Aug-2020	Procedures for Emergency Unblinding, 6.7	Clarification of wording to emphasize that the investigator has the final decision and unilateral right for unblinding.
5 / CSP V4.2	04-Aug-2020	Assessment of Adverse Events, 9.3.4	Update of section "Responsibilities of Sponsor" to change the Reference Safety Information (RSI) for cryoprecipitate.
			Reference to the new Reference Safety Information for cryoprecipitate (section 4.8 of the SmPC of PPD solution for infusion).
5 / CSP V4.2	04-Aug-2020	Pregnancy, 9.3.8.1 (Gender Distribution 4.1.1)	Adding of a list of reliable birth control methods.
6 / CSP V4.3	06-Sep-2021	III Flowchart	Reintroduction of urinalysis on follow-up day 5 in the flowchart as this item was deleted in the CSP V3.0 by mistake.
			Adaption of footnotes:
			
 
Option for rescheduling tests and procedures that require an in-person visit from Day 36 (closing visit) to the day of discharge from hospital.
 

			
 
Inclusion of missing footnote for coagulation factors on day 1, end of surgery.
 

Amendment No / CSP Version	Date	Sections concerned	Rationale
6 / CSP V4.3	06-Sep-2021	7.1 Visit Schedule for PMP subjects	Option for using a phone call instead of an in-person closing visit is depicted.
		7.2 Duration of the Clinical Study	Option for rescheduling tests and procedures that require an in-person visit from Day 36 (closing visit) to the day of discharge from hospital is depicted.
6 / CSP V4.3	06-Sep-2021	9.2.1.4 Laboratory Parameters	Clarification regarding increased laboratory parameter values (liver function tests) and the documentation as adverse events.
6 / CSP V4.3	06-Sep-2021	3, 5.2.1, 7.1, 9.1.2, 10.1	Editorial changes.

Study No.: 995	Final 4.3_UK	Clinical Study Protocol
EudraCT No.: 2017-001163-20		06-SEP-2021
CONTRACTOR AND A LEADER FOR LL CORT LAND FOR	and a way to be a feature of a large to be to be an all as an access of an experimental strategy and an experimental strategy of the second	UQ.

# II. STUDY SYNOPSIS

Title	A randomized, active-controlled, multicenter, phase III study investigating efficacy and safety of intra-operative use of BT524 (human fibrinogen concentrate) in subjects undergoing major spinal or abdominal surgery (AdFIrst)						
Clinical Phase	111						
Coordinating Investigator	PPD						
Study Objectives	The main purpose of this phase III study is to demonstrate the efficacy of BT524 as a complementary therapy to management of uncontrolled severe hemorrhage in subjects undergoing elective major spinal or abdominal surgery. The primary objective of this study is to demonstrate that BT524 is non-inferior that means not worse than fresh frozen plasma (FFP)/cryoprecipitate with a non-inferiority margin of 150 mL in reducing intra-operative blood loss by intravenous (IV) administration in subjects with acquired hypofibrinogenaemia undergoing elective major spinal or abdominal surgery. If therapeutic equivalence (non-inferiority) has been demonstrated, therapeutic superiority of BT524 compared with FFP/cryoprecipitate will also be assessed. Secondary objectives are to demonstrate the efficacy of BT524 by assessing the correction of the fibrinogen level intra-operatively, the transfusion requirements, post- operative blood loss in the first 24 hours, the number of subjects with rebleeds, the hospital length of stay and the in- hospital mortality. Secondary objectives also comprise the safety of BT524 by documenting the number of adverse events (AE) including changes in laboratory parameters, the viral status, and the frequency and severity of thrombosis and of thromboembolic events (TEEs).						
Study Design	Prospective, randomized, active-controlled, multicenter, non- inferiority study						
Study Population	In the United Kingdom: Adult subjects (≥ 18 years) of both gender undergoing elective abdominal surgery with expected major blood loss						
Inclusion Criteria	
 
At screening:
 
1. Written informed consent
 
2. Subjects scheduled for elective cytoreductive pseudomyxoma peritonei (PMP) surgery with expected major blood loss
 
3. Male or female, aged ≥ 18 years
 
4. No increased bleeding risk as assessed by standard coagulation tests and medical history
 
						

	
 
Intra-operative trigger for treatment:
 
Intra-operative prediction of clinically relevant bleeding of > 2 L, requiring hemostatic treatment during surgery.
 
			
Exclusion Criteria	
 
Pregnancy or unreliable contraceptive measures or breast feeding (women only)
 
Hypersensitivity to proteins of human origin or known hypersensitivity reactions to components of the Investigational Medicinal Products (IMP)
 
Participation in another clinical study within 30 days before entering the study or during the study and/or previous participation in this study
 
Treatment with any fibrinogen concentrate and/or fibrinogen-containing product within 30 days prior to infusion of IMP
 
Employee or direct relative of an employee of the Contract Research Organization (CRO), the study site, or Biotest
 
Inability or lacking motivation to participate in the study
 
Medical condition, laboratory finding (e.g. clinically relevant biochemical or hematological findings outside the normal range), or physical exam finding that in the opinion of the investigator precludes participation
 
Presence or history of venous/arterial thrombosis or TE in the preceding 6 months
 
			
Number of Subjects	100 evaluable subjects per treatment arm			
Countries / Number of Study Sites	Multicenter, multinational, Europe / 15-20 sites EU and Switzerland: Spine surgery, FFP as comparator United Kingdom (one site): PMP surgery, cryoprecipitate as comparator			
Investigational Medicinal Products (IMP)	
 
BT524 (human fibrinogen concentrate) and cryoprecipitate
 
BT524 is a heat-treated, lyophilized fibrinogen concentrate manufactured from human plasma.
 
BT524 is presented as a single-use vial containing 1 g of lyophilized fibrinogen. The lyophilisate is to be reconstituted with 50 mL of water for injections, resulting in a final concentration of 20 mg/mL for IV infusion.
 
FFP refers to the liquid portion of human blood that has been frozen and preserved after a blood donation and will be used for blood transfusion.
 
Cryoprecipitate is made from FFP which is frozen and repeatedly thawed in a laboratory to produce a source of concentrated clotting factors including fibrinogen, factor VIII, factor XIII, von Willebrand factor (vWF) and fibronectin and platelet microparticles.
 
			

<sup>1 Approximately 60 minutes after the start of cytoreductive PMP surgery.

Dosage and Mode of Administration	
 
Subjects undergoing cytoreductive PMP surgery: BT524, administered intravenously: Fixed first dose of 4 g, subsequent intra-operative infusions (4 g) as required.
 
Cryoprecipitate, administered intravenously: Therapeutic dose is 2 pools, each pool consisting of 5 units (10 units, dose-equivalent to 4 g fibrinogen concentrate), subsequent intra-operative infusions of 2 pools as required.
 
				
Duration of Treatment	
 
Single or repeated intra-operative administration of IMP.
 
Follow-up per subject:
 
Each subject will be followed for at least 5 weeks, with clinical and laboratory data collected on visits scheduled on
 
				
	Days 2, 3, 5 and 8, and the closing visit, scheduled on Day 36* after the day of surgery (*+35, up to Day 71 if required).				
Criteria for Evaluation					
- Efficacy	
 
Primary Endpoint:
 
Intra-operative blood loss after decision to treat the subject with IMP until the end of surgery as measured by amount of blood from the blood suction unit and amount of blood from swabs, surgical cloths and compresses.
 
				
	
 
Secondary Endpoints:
 
Proportion (%) of subjects with successful correction of fibrinogen level 15 minutes after start of first IMP administration
 
Time to first successful correction of fibrinogen level
 
Total amount of transfusion products (allogenic blood products) or autologous blood transfusion infused after start of first IMP administration until end of surgery
 
Amount of red blood cells (allogenic and autologous RBCs) infused after start of first IMP administration until end of surgery
 
Post-operative blood loss in the first 24 hours
 
Proportion (%) of subjects with rebleeds after the end of surgery until Day 8
 
Hospital length of stay after surgery
 
In-hospital mortality
 
				
- Safety	
 
Secondary Endpoints:
 
AEs
 
Changes in vital signs
 
Changes in clinical laboratory assessments of hematology, clinical chemistry, and urinalysis
 
Changes in clinical laboratory assessments of markers of coagulation
 
				

	
 
Changes in clinical laboratory assessments of coagulation factors
 
Frequency and severity of thrombosis and of TEEs
 
Viral status
 
					
Biostatistical Concept	Assuming a blood loss of about 500 mL in the FFP  -/ cryoprecipitate-treatment arm after the decision to treat the subject with IMP until the end of surgery, a standard deviation of 375 mL, a non-inferiority margin of 150 mL, and an alpha-level of 2.5% (1-sided) 100 evaluable subjects per treatment arm are needed to demonstrate the non-inferiority of BT524 by using a t-test with 80% power. The sample size was calculated with nQuery Advisor Version 4.0 or higher. Primary Endpoint:					
	The primary endpoint is intra-operative blood loss after the decision to treat the subject with IMP until the end of surgery. The primary analysis of this endpoint will test for non-inferiority. The final analysis will be performed using analysis of covariance (ANCOVA) with the predictive block loss (> 1,000 mL to $\leq$ 2,000 mL and > 2,000 mL) as a covariate. Non-inferiority will be demonstrated if the upper confidence limit of the 2-sided 95% confidence interval for the difference in the least square means is less than the non-inferiority margin (150 mL). If non-inferiority is demonstrated, then superiority will be assessed.					
	Interim analyses: In this study, 3 interim analyses with an alpha-adjustment according to Haybittle/Peto ( Haybittle, 1971; Peto et al., 1976; Schulz and Grimes, 2005 ) are planned. This leads to local alpha levels of 0.001 for each interim analysis, a significance level of 0.05 for the final analysis, and to an overall global alpha level of 0.05. All interim analyses will be based on the per-prototocl set. The first interim analysis is planned with approximately 50 spine subjects, the second one with at least 40 PMP subjects and all other evaluable spine subjects at that time- point. The third interim analysis is planned with approximately 80% of subjects of the total sample size.					
	Aim of all interim analyses is to adapt the sample size according to the observed blood losses and the standard deviations:					
	
 
a.) Early termination due to non-inferiority of BT524 in comparison with the used standard therapies.
 
b.) Continuation with the sample size as initially planned.
 
c.) Adjustment of sample size to take into account changes from the previous assumptions on the additional blood loss.
 
					

 $^{2}$  FFP treatment is not applicable for subjects in the UK.

	
 
d.) Stopping the study early due to futility if the sample size re-estimation indicates a much higher number than planned before.
 
						
	Secondary Endpoints:						
	All secondary efficacy endpoints will be summarized descriptively by treatment arm.						
	The secondary endpoints of proportion of subjects with a successful correction of fibrinogen level and proportion of subjects with rebleeds will be compared between the treatment arms using a Cochran-Mantel-Haenszel (CMH) approach stratified by predictive blood loss.						
	The secondary endpoint 'time to first successful correction of fibrinogen level' will be compared between the treatment arms using a Chi-Square test.						
	The secondary endpoints of consumption of transfusion products, amount of RBCs and post-operative blood loss in the first 24 hours will be analysed using ANCOVA with the predictive blood loss as a covariate.						
	Safety will be assessed based on AEs, laboratory data, vital signs data, frequency and severity of thrombosis and of TEE and viral status which will be summarized descriptively.						
	Data Safety Monitoring Board:						
	An independent Data Safety Monitoring Board (DSMB) will review unblinded safety data at regular intervals during the study.						
	Data Monitoring:						
	After 40 subjects have completed, the overall mean and standard deviation of the primary endpoint will be derived using blinded data of all 40 subjects without separating according to treatment to assess if the sample size needs to be adjusted.						
First Subject In	Q1 2018						
Last Subject Last Visit (planned)	Tbd						

# III. FLOWCHART OF STUDY

Study Schedule Day	D-42 to D-1	D-2 to D1	D1	D1	D1	D1	D2	D3	D5	D8	D36 (+35)
Assessments Visit		Prior	Surgery			Follow-	Follow-	Follow-	Follow-		
	Screening	surgery (Baseline)	prior 1 st dose	pre- dose	post- dose	end of surgery	up	up	up	up	Closing
Informed consent	•										
Check/re-check of inclusion / exclusion criteria	•	• 									
Demographic data	•										
Classification of type of surgery	•										
Recording expected blood loss		•									
Body weight	•	•2									
Physical examination	•	•2					•	•	•	•	•3
Pregnancy test, only in females of childbearing potential	•	•2									
Medical and surgical history	•	•4									
Viral safety: Collection of retention sample	•										• 
Virus serology (hepatitis B, hepatitis C, HIV)	•										• 
Vital signs	•	•	•	•	•	•	•	•	•	•	• 
Hematology and clinical chemistry	•	•2	•			•	•	•	•	•	• 
Urinalysis	•	• 					•	•	•	•	• 
Markers of coagulation (coagulation activation tests)	•	•2	•		•5	•6	•	•	•	•	• 
Plasma concentration of fibrinogen activity (Clauss assay)	•	•2	•		•5	•6	•				
FIBTEM A10 (ROTEM)	•	•2	•	٠	•5	•6	•				
Maximum clot firmness (MCF) (ROTEM)	•	•2	•	•	•5	•6	•				

<sup>1 Diagnostic tests will be repeated at the investigator's discretion.

<sup>2 Diagnostic tests have to be done prior to surgery. In case of short time-period between screening and baseline (≤ 2 days) these tests have only to be repeated based on medical judgment of the investigator. If not repeated, screening results will serve as baseline.

<sup>3 Diagnostic tests are required as part of the closing visit. In case the closing visit is scheduled as a phone call, these tests can be performed on the day of hospital discharge.

<sup>4 Previous medication: change from screening.

<sup>5 Tests have to be done only 15 and 90 minutes after start of 1st IMP administration.

<sup>6 Tests (*Markers of coagulation, Clauss assay, FIBTEM A10, MCF, coagulation factors*) have to be done '90 min after start of 1st IMP administration' and at the 'end of surgery'. In case of a short time-period between these two time points (<30 min) these tests have only to be repeated based on medical judgment of the investigator.

Study Schedule Day	D-42 to D-1	D-2 to D1	D1	D1	D1	D1	D2	D3	D5	D8	D36 (+35)
		Screening Prior surgery (Baseline) 1	Surgery			Follow-	Follow-	Follow-	Follow-		
Assessments Visit	Screening		prior 1 st dose	pre- dose	post- dose	end of surgery	up	up	up	up	Closing
Coagulation factors (including vWF)		•	•		•7	•6					
Intra-operative inclusion criteria			•								
Intravenous infusion(s) of IMP (BT524 or cryoprecipitate)				•8							
Recording start/end of surgery			•			•					
Continuous measurement of blood loss from start of surgery				٠		•	•				
Calculation and recording of blood loss						•9	● 				
Recording time of decision to treat the subject with IMP			•								
Order of IMP			•	٠							
Randomization			•								
Rebleeding episodes						•	•	•	•	•	
Concomitant medication or treatment				•		•	•	•	•	•	•
Transfusion products				٠		•	•	•	•	•	•
Adverse events	•	•		•		•	•	•	•	•	•

 <sup>7 Test has to be done only 90 minutes after start of 1st IMP administration.
  Total volume and total infusion time (start and end of each infusion) to be recorded.

 <sup>9 Intra-operative blood loss from time point of decision to treat the patient with IMP until end of surgery.
  Recording of blood loss (drainage volume) until 24 hours after end of surgery.

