# Follow-up Visit Day 2:

All subjects treated with IMP will attend the follow-up visit one day after surgery (Day 2). The following procedures will be performed:

- Continuous measurement of post-operative blood loss (drainage volume) and recording until 24 hours after end of surgery.
- Physical examination will be performed.
- **Vital signs** (including pulse [heart rate], blood pressure, respiratory rate, body temperature) will be recorded.
- Sample for **coagulation activation tests** (PT(INR), aPTT, TAT, F1+2, D-dimer, PS, PC, AT III, TT, TGT) will be taken.
- Samples for **clinical laboratory parameters** (hematology, clinical chemistry, urinalysis) will be taken:
  - **Hematology** (RBC, WBC, platelet count, hemoglobin, hematocrit)
  - Clinical chemistry (ASAT, ALAT, creatinine, creatinine clearance, BUN/Urea, γ-GT, AP, total bilirubin, potassium, sodium, calcium, chloride)
  - **Urinalysis** (pH, blood, WBC, protein, glucose, ketone bodies, nitrite, bilirubin, urobilinogen)
- Sample for plasma activity of fibrinogen (Clauss assay) will be taken and
- FIBTEM A10 and MCF (ROTEM) will be performed.
- Transfusion products (allogenic blood products) will be documented.
- **Concomitant medication or treatment** will be documented. The type of concomitant medication/treatment, dose/schedule, duration, and the indication the concomitant medication/treatment was given for will be documented.
- **AEs** will be documented.
- **Rebleeding episodes** will be recorded.

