#### Postoperative Blood Loss (Drainage Volume)

The plasma drainage tube and disposable drainage bag will be emptied 24 hours after the end of the surgery. The end of surgery is defined as time of last suture. The drainage volume will be measured and postoperative blood loss will be recorded.

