#### 9.1.3.2 Specification of Secondary Efficacy Endpoints

• Proportion (%) of subjects with successful correction of fibrinogen level 15 minutes after start of first IMP administration.

Successful correction of fibrinogen level in a subject is defined as restoring fibrinogen FIBTEM A10 baseline level to at least 95% measured by ROTEM 15 minutes after start of first IMP administration. A correction of at least 95% is considered successful, as measurement methods has a coefficient of variation of about 5% (Solomon et al., 2015).

- Time to first successful correction of fibrinogen level (15 minutes or 90 minutes after start of first IMP administration, end of surgery, not within surgery).
- Total amount of transfusion products (allogenic blood products) or autologous blood transfusion infused after start of first IMP administration until end of surgery. The end of surgery is defined as time of last suture.

- Amount of RBCs (allogenic and autologous) infused after start of first IMP administration until end of surgery. The end of surgery is defined as time of last suture.
- Post-operative blood loss in the first 24 hours.
- Proportion (%) of subjects with rebleeds. Rebleeds are defined as any bleed requiring hemostatic treatment (including reoperation) after the end of surgery until Day 8.
- Hospital length of stay after surgery, defined as the date of discharge minus the date of surgery.
- In-hospital mortality.

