8.9 End of Surgery

End of surgery is defined as time of last suture.

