8.15 Post-operative Blood Loss in the First 24 hours

The plasma drainage tube and disposable drainage bag will be emptied 24 hours after the end of surgery. The post-operative drainage volume in the first 24 hours is collected in eCRF.

8.16 Rebleeds after the End of Surgery until Day 8

Rebleeds are defined as any bleed requiring hemostatic treatment (including reoperation) after the end of surgery until Day 8, which are recorded in eCRF.

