12.5.3.4 Post-operative Blood Loss

The post-operative blood loss in the first 24 hours is the blood loss from end of surgery until 24 hours after end of surgery. This secondary efficacy endpoint will be descriptively summarized by treatment arm.

An ANOVA analysis will be performed with the post-operative blood loss in the first 24 hours as the dependent variable and the predictive blood loss (> 1,000 mL to \leq 2,000 mL and > 2,000 mL) as a covariate. The least square means and difference (BT524 versus FFP/cryoprecipitate) in least square means will be presented with the corresponding 95% confidence intervals and 2-sided p-value. This will be repeated by surgery type.

A box-whisker plot for post-operative blood loss will be generated for both treatment arms.

In addition, a subgroup analysis of the post-operative blood loss in the first 24 hours will be performed for the FAS. Subgroups are spinal and abdominal surgery. The post-operative blood loss will be analyzed using an ANOVA for each subgroup. The least square means and difference of least square means together with 95% confidence intervals and p-values for each subgroup will be presented.

Post-operative blood loss will be listed for the FAS.

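### The 24-hour post-operative blood loss endpoint counts drain content only, so subjects re-operated for bleeding or dead within 24 hours can be understated or dropped

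*Protocol*

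**What the plan says.** Every operational description of this endpoint uses the drain and nothing else:

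- Protocol flowchart, footnote 10: "Recording of blood loss (drainage volume) until 24 hours after end of surgery".
- Protocol 7.1, Follow-up Visit Day 2: "Continuous measurement of post-operative blood loss (drainage volume) and recording until 24 hours after end of surgery".
- Protocol 9.1.2.2, after stating that the drain and bag are emptied at 24 hours: "The drainage volume will be measured and postoperative blood loss will be recorded".
- SAP 8.15: "The post-operative drainage volume in the first 24 hours is collected in eCRF".

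SAP 12.5.3.4 describes the quantity to be analysed by its time window: "The post-operative blood loss in the first 24 hours is the blood loss from end of surgery until 24 hours after end of surgery". It enters an ANOVA with predictive blood loss as covariate, and a between-arm difference, confidence interval and p-value are reported for the FAS.

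The plan foresees bleeding that sends a subject back to theatre. Protocol 9.1.3.2 states: "Rebleeds are defined as any bleed requiring hemostatic treatment (including reoperation) after the end of surgery until Day 8". SAP 12.5.3.5 analyses these rebleeds as a proportion of subjects and as a count.

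**The concern.** The value is a drainage volume but is named, analysed and read as blood loss. The two part company in a subject who bleeds enough to be re-operated within 24 hours. What is suctioned, swabbed or evacuated at that operation does not pass through the drain, and no rule adds it. A subject who dies before 24 hours has no stated value at all.

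The omission depends on the outcome: it happens because the subject bled badly. Protocol section 2 lists 24-hour post-operative blood loss among the secondary objectives meant to show the efficacy of BT524. If one arm had more early re-operations or deaths, that arm's mean on this endpoint would look better than it should, and the comparison could shrink or reverse.

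**Working it through.** **Does any rule bring the uncounted blood back in?**

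1. Suction and swab measurement. SAP 8.11 limits it, for the primary endpoint, to the time from decision to treat to end of surgery. SAP 8.9 fixes that end: "End of surgery is defined as time of last suture". A later re-operation lies outside it.
2. Other sources. The intra-operative formula in SAP 8.11 has a term for blood loss from other sources. SAP 8.15 has no such term.
3. Missing data. Protocol 10.3 does not impute continuous efficacy endpoints. SAP 8.4 considers imputation only when at least 10% of data are missing, with a worst-case method as a sensitivity analysis. A re-operated subject's value is present but incomplete, so neither rule applies.
4. Rebleeds. SAP 12.5.3.5 reports subjects and events up to Day 8. It returns no millilitres to the 24-hour value and does not separate the first 24 hours.
5. Death before 24 hours. The documents are silent. The value may be a short-window volume or may be missing. If missing, the subject drops out of the ANOVA.

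**Size**

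The plan states no mean, SD, power or re-operation rate for this endpoint, so there is no figure to reproduce. The rates, volumes and SD below are assumptions.

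Let r be the share of an arm re-operated for bleeding within 24 hours, and V the mean volume lost outside the drain at re-operation, taken as equal in both arms.

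- Understatement of an arm mean = r × V. At 5% and 1,000 mL this is 0.05 × 1,000 = 50 mL. Over r = 2% to 10% and V = 500 to 2,000 mL it runs from 0.02 × 500 = 10 mL to 0.10 × 2,000 = 200 mL.
- Bias in the difference BT524 minus comparator = −(r_BT524 − r_comparator) × V.
  - 5% against 2%: −0.03 × 1,000 = −30 mL and −0.03 × 1,500 = −45 mL. For V from 500 to 2,000 mL: −15 to −60 mL.
  - 10% against 5%: −0.05 × 500 = −25 mL to −0.05 × 2,000 = −100 mL.
  - 2% against 5%: +15 to +60 mL for the same V, now against BT524.
  - Equal rates: 0 mL.

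To judge scale, assume an SD of 300 mL and 100 subjects per arm. The SE of the difference is 300 × √(2/100) = 42.4 mL, so 30 to 45 mL is 0.7 to 1.1 SE. Adding the uncounted blood would also widen the spread. If it is independent of drainage, each arm's variance grows by r(1 − r)V²:

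- V = 1,000 mL: SE = √[(90,000 + 47,500)/100 + (90,000 + 19,600)/100] = 49.7 mL, ratio 30/49.7 = 0.6.
- V = 1,500 mL: SE = √[(90,000 + 106,875)/100 + (90,000 + 44,100)/100] = 57.5 mL, ratio 45/57.5 = 0.8.

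For early death, if the value kept is what drained until then and drainage is constant (assumed), death at 6, 12 or 18 hours leaves 25%, 50% or 75% of the window recorded.

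**The case against.** The strongest reply is that this is an openly declared drainage measure, and that the affected subjects are visible elsewhere. Rebleeds including re-operation are a secondary endpoint with a CMH comparison, relevant bleeding complications are adverse events of special interest, and in-hospital and overall mortality are tabulated by arm. SAP 12.5.2 calls all secondary analyses exploratory, and no decision rule uses this volume. All of that stands, and it limits the weight of the point. It does not repair the volume itself, which still carries a p-value under the name of blood loss.

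A reader might infer four stronger things that the documents do not support:

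- **That the SAP contradicts the protocol by promising all blood lost.** SAP 12.5.3.4 sets a time window and does not say that every source is counted. The gap is between label and measurement.
- **That the endpoint favours BT524.** No re-operation or death rates are given. The bias can go either way, and it is zero with equal rates and volumes.
- **That a subject who dies early is scored on a short-window volume.** The value could equally be missing.
- **That re-operation blood loss can simply be added.** Neither document shows that this volume is collected; only the rebleed event is.

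Drain fluid is also counted as blood with no correction for other fluid, which could push values up. So the understatement concerns the uncounted part, not necessarily a subject's whole value.

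**Conclusion.** The point holds in a limited form. The 24-hour endpoint is drain content read as blood loss. It leaves out blood lost outside the drain at an early re-operation, and it has no rule for death before 24 hours. Whether the treatment comparison is distorted depends on a between-arm difference in those events or in the volumes lost. The documents fix neither its size nor its direction.

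The 30 to 45 mL illustration, about 0.6 to 1.1 SE depending on which SE is used, rests wholly on the assumed rates, volumes and SD. The primary endpoint, margin and sample size are untouched. This is a cheap improvement, between optional and recommended.

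**What to change.** In SAP 8.15 and 12.5.3.4, before database lock:

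1. Keep drainage volume as the measured value and label it 24-hour drainage volume in text and tables.
2. Add a supportive van Elteren test, stratified by predictive blood loss, in which subjects re-operated for bleeding or dead within 24 hours of last suture take the worst rank. SAP 12.5.1.4 already provides this method for the primary endpoint. Rebleeds, concomitant procedures and deaths are already recorded. State which recorded date or time decides the 24-hour cut.
3. Show the number of such subjects by arm with the table, and say how many had no drainage value.
4. Add re-operation blood volume only if it proves to be documented already, and then as a sensitivity analysis.

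The cost is some SAP wording, one count and one supportive analysis, with no new measurement for items 1 to 3. The drawback is that the rank analysis gives no estimate in millilitres, so it sits beside the ANOVA and does not replace it.
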